### k. Safety Oversight:

The Vanderbilt-Ingram Cancer Center (VICC) oversees patient safety and data monitoring for its investigator-initiated and NIH-NCI funded clinical trials through its Data and Safety Monitoring Committee (DSMC). The Committee maintains authority to intervene in the conduct of studies as necessary to ensure clinical research performed at VICC achieves the highest quality standards.

## I. Data and Safety Monitoring Committee/Quality Assurance:

The Vanderbilt-Ingram Cancer Center (VICC) oversees patient safety and data monitoring for clinical trials through the Data and Safety Monitoring Committee (DSMC). The committee will convene on a quarterly basis and *ad-hoc* as necessary. The DSMC provides oversight of the internal audit function. During audits the

## Comparison of High vs. Standard Dose Flu Vaccine in Pediatric Stem Cell Transplant Recipients

DMID Protocol Number 16-0117

Protocol Version 8.0

Date: 9/12/2019

Quality Assurance (QA) auditor will review selected case histories. In addition they will conduct a regulatory and pharmacy audit as needed. The data presented to the DSMC will be blinded unless the committee requests un-blinded data. The DSMC will determine if the findings in the audit report require a response from the Principal Investigator. After reviewing submitted corrective action plans, the committee has the authority to approve the continuation of the study, increase the frequency of auditing, suspend accrual, or terminate a protocol; however, this will be in discussion with the DSMB.

This trial will be monitored continuously by the study's principal investigator and on a weekly and monthly basis by the Research Team. Quarterly safety and monitoring reports are available to the DSMC. The DSMC reviews all serious adverse events reported during the previous quarter for all clinical trials active at the VICC and makes recommendations to address concerns of patient safety. Since data from REDCap will be transferred to Oncore, the DSMC will be able review all safety data from all nine sites.

A Quality Assurance auditor under the direction of the DSMC will audit this clinical trial quarterly for compliance with adverse event reporting, regulatory and studies requirements, and data accuracy and completion. Audit reports detailing the findings are provided to the DSMC.

Any DSMC communications regarding safety evaluations will be shared with the Chair of DSMB and the DSMB. This information will also be shared with FDA-CBER and NIH.

### **m. Blinding:**

All study staff, subjects, and their parent/guardians will be blinded to which vaccine the subject will receive, except for an un-blinded vaccinator. This individual will not inform the study team, subjects, and/or their parent/guardians which vaccine they administered to the subject. The un-blinded vaccinator will not participate in any other study activities. If the study vaccine is provided in a blinded manner, then research staff will be able to administer the vaccine, and an un-blinded vaccinator will not be necessary. The pharmacy will be un-blinded and will have a record of which vaccine was given to each subject.

### **n. Vaccine Labeling Plan:**

The following statement will be used: "Caution: New Drug – Limited by Federal (or United States) law to investigational use" and subjects and parents/guardians will be informed of this during the consent process.

## **17. Statistical Considerations:**

- a. **Sample Size Calculations:** A total of 200 children will be targeted, with 100 in each group. This is based on the assumption, with 80% power, that 20% of the children in the standard dose group will achieve a protective titer compared to 40% of the HD-TIV group for at least one influenza antigen. Accounting for a 20% drop out rate, 100 children in each group will be needed.

Strain	Expected Seroprotection HD-TIV	Expected Seroprotection standard dose	N (HD)	N (SD)	Power	Total N with 20% drop out
Expected HD-TIV seroprotection is twice as of standard dose						
A	40%	20%	80	80	80%	200
A	50%	25%	55	55	80%	138
A	60%	30%	40	40	80%	100
A	70%	35%	28	28	80%	70

- b. **Immunogenicity analysis:** The probability of achieving a 4-fold (or greater) rise in post-vaccination HAI titers relative to baseline, as well as the probability of a HAI titer greater than

1:40, will be estimated using a binomial model. We will calculate the Bayesian posterior distribution of the probabilities under all 4 combinations of standard and HD-TIV crossed with a single dose and two doses. From these probabilities, odds ratios will be calculated along with 95% credible intervals. These quantities will be modeled as a logit-linear function of several covariates, including CD4+/CD8+/CD19+ and IgG levels, absolute neutrophil and lymphocyte count (or their ratio), time from post-transplant to enrollment, type of preparative regimen, donor status, and stem cell source. In addition, the distributions of geometric mean HAI titers for high and standard dose recipients will be estimated via log-normal models and expressed as ratios in order to evaluate the evidence for higher GMT in the HD-TIV sample, after one and two vaccines. In addition, we will compare each group to document if they meet serological criteria by WHO biological standards for influenza vaccines (>40% for seroconversion, GMT >2.5-fold increase, and >70% with  $\geq 1:40$ ).

- c. **Safety analysis:** For the primary analysis of the safety data, the proportion of subjects in each group experiencing at least one solicited AE will be calculated along with 95% posterior credible intervals. The difference between the rates of solicited AEs between the groups will be estimated by calculating the posterior 95% credible interval of the difference in proportions. For each group and each event, solicited and unsolicited AEs will be descriptively summarized. Severities of solicited and unsolicited AEs will also be descriptively summarized for each group and each type of event. Descriptive statistics will include number experiencing event, mean and 95% posterior credible interval. Maximum size of redness and swelling may be descriptively summarized for each group and event; proportion of events lasting longer beyond Day 3 may also be descriptively summarized.
- d. **Specific B and T cells responses:** We will estimate the association between HAI titers and expression of ICOS and CD40L on CD4+CXCR5+ T cells. We anticipate that the frequency of circulating TFH cells with expression of ICOS and CD40L will directly correlate with higher influenza titers. We will also estimate the association between HAI titers and the distribution of circulating plasmablasts (CD19+CD27+CD38+), using either parametric linear models or Gaussian processes if the relationship cannot adequately be modeled linearly. In addition to the phenotypic analysis, we will perform in vitro stimulation of PBMC with influenza antigen. We will measure the degree of ICOS and CD40L expression of CD4+CXCR5+ T cells in the presence or absence of antigen, and model the relationship between response and HAI titer, where we predict responders to have higher HAI titers. Comparisons between marker expression on CD4+CXCR5+ T cells in the presence or absence of antigen and correlations between HAI titer and Marker expression on CD4+CXCR5+ T cells will be evaluated by building models that regresses T cell counts on HAI titers. We will compare both linear and non-linear fits to the data, and choose the optimal model as determined by a model selection criterion, such as AIC. Should the parametric models not adequately fit the data, we will use a semi-parametric regression via Gaussian processes as a robust alternative.
- e. **Influenza-Like-Illness assessment.** The percentage of individuals in each group that test positive for influenza by PCR and the number of ILIs in each group during the influenza season will be compared.

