**b. Secondary Objectives:**

- To determine whether HD-TIV compared with standard dose QIV will increase the probability of achieving a  $\geq 4$ -fold rise in HAI titers,  $\geq 1:40$  HAI titer, or higher GMT titers to influenza B antigens in pediatric HSCT recipients.
- To determine the frequency and severity of solicited local injection site adverse events (e.g. pain/ tenderness, redness, and swelling/Induration at injection site) with HD-TIV compared to standard QIV in pediatric HSCT recipients.
- To determine the frequency and severity of solicited systemic adverse events (e.g. fevers, headache, fatigue/malaise, nausea, body ache/myalgia, general activity level, and vomiting) with HD-TIV compared to standard dose QIV in pediatric HSCT recipients.
- To define the relationship between HAI titers, ex-vivo T and B cell phenotype, and ex-vivo influenza-specific T and B cell response in pediatric HSCT recipients receiving either HD-TIV or standard dose QIV.
- To correlate HAI responses to MN responses.
- To compare the persistence of HAI and MN titers for all four antigen seven months after the last vaccine dose.
- To compare influenza detection by PCR during influenza season in pediatric HSCT recipients receiving either HD-TIV or standard dose QIV.
- To assess HAI and MN response in children undergoing two consecutive years of vaccination using the same antigen dose.
- To evaluate neuraminidase inhibition titers (NAI) responses in children undergoing two consecutive years of vaccination and correlate them to HAI responses.

**3. Study Area:** The study will be conducted in the Outpatient Pediatric Oncology/HSCT Clinics or Clinical Trial Centers at the following sites: Table 2 includes yearly average number of HSCT transplants per site (**Table 2**).**Table 2. Sites and Average Number of Yearly Allogeneic Transplants**

Site	Average Number of Yearly transplants	Potential During Study Period
Children's Mercy Hospital	25	56
Columbus Nationwide Children's Hospital	25	56
Vanderbilt University	30	68
Children's Hospital of Philadelphia (CHOP)	35	79
Seattle Children's Hospital	50	113
St. Jude Children's Research Hospital	50	113

**Comparison of High vs. Standard Dose Flu Vaccine in Pediatric Stem Cell Transplant Recipients****DMID Protocol Number 16-0117****Protocol Version 8.0**

Date: 9/12/2019

UCSF (University of California San Francisco)	50	113
Benioff Children's Hospital		
Cincinnati Children's Hospital	90	203

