1.2 Study objectives

Immunogenicity and safety objectives are organized into subsections below. To avoid repetitive language, *all* objectives apply to the target study population (namely, pediatric HSCT recipients).

1.2.1 *Objectives for HAI immunogenicity outcomes*

The primary objective is to determine whether two doses of HD-TIV is associated with a higher geometric mean HAI titer to either influenza A antigen (H1N1 and H3N2, evaluated separately) compared to two doses of SD-QIV.

The secondary objectives pertaining to HAI immunogenicity outcomes are as follows:

- To determine whether two doses of HD-TIV is associated with a higher geometric mean HAI titer to influenza B antigens as compared to two doses of SD-QIV.
- To determine whether two doses of HD-TIV is associated with higher odds of seroconversion or seroprotection in *any* HAI antigen as compared to two doses of SD-QIV.
- To compare HAI immunogenicity for each antigen between the following groups: (a) one dose of HD-TIV vs. one dose of SD-QIV, (b) one dose of HD-TIV vs. two doses of HD-TIV, and (c) one dose of SD-QIV vs. two doses of SD-QIV.

The tertiary objectives pertaining to HAI immunogenicity outcomes are as follows:

- To compare HAI immunogenicity for each antigen between the one dose of HD-TIV and two doses of SD-QIV.
- To determine whether time post-transplant, subject age, or GVHD status (presence/absence) modifies the association between vaccination group and HAI response.
- To characterize the relationship between HAI titers, ex-vivo T and B cell phenotype, and ex-vivo influenza-specific T and B cell response in subjects receiving either HD-TIV or SD-QIV.
- To compare HAI immunogenicity outcomes between treatment groups (one dose or two doses of HD-TIV vs. one dose or two doses of SD-QIV, respectively) among those enrolled for a second year (repeaters).

1.2.2 *Objectives for safety outcomes*

The primary objectives for safety outcomes are to compare the frequency/severity of solicited local injection site adverse events (AEs) and systemic AEs between HD-TIV and SD-QIV following the first dose and following the second dose. The secondary objective is to compare safety outcomes between treatment groups among those enrolled for a second consecutive year (repeaters).

1.2.3 *Further exploratory objectives*

- To compare the persistence of HAI and microneutralization (MN) titers between HD-TIV and SD-QIV across all four antigens seven months after the final vaccine dose.

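### Protocol 17.d evaluates marker expression with versus without influenza antigen by a regression on HAI titer that has no antigen term, and the SAP supplies no replacement

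*Protocol*

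**What the plan says.** Protocol 17.d describes an in vitro stimulation experiment: "We will measure the degree of ICOS and CD40L expression of CD4+CXCR5+ T cells in the presence or absence of antigen". It then links the readout to serology: "model the relationship between response and HAI titer, where we predict responders to have higher HAI titers".

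The next sentence gives the method. Its subject covers two questions: "Comparisons between marker expression on CD4+CXCR5+ T cells in the presence or absence of antigen and correlations between HAI titer and Marker expression" on those cells. Both, it says, "will be evaluated by building models that regresses T cell counts on HAI titers".

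Two provisions on model form follow. The first is "We will compare both linear and non-linear fits to the data, and choose the optimal model as determined by a model selection criterion, such as" (the example given there is AIC). The second applies if the parametric models fit poorly: "we will use a semi-parametric regression via Gaussian processes as a robust alternative".

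The protocol's secondary objective is "To define the relationship between HAI titers, ex-vivo T and B cell phenotype, and ex-vivo influenza-specific T and B cell response". Hypothesis 3 in section A goes further and predicts higher influenza-specific B and T cell responses with HD-TIV than with standard-dose QIV.

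SAP 1.2.1 keeps, as a tertiary objective, the relationship of HAI titers to phenotype and to "ex-vivo influenza-specific T and B cell response in subjects receiving either HD-TIV or SD-QIV". SAP section 5 is introduced as covering every objective in 1.2.1, but 5.1 to 5.5 contain no cell analysis. The only one is in 7.5, which asks whether baseline phenotype predicts HAI titers after vaccination and uses FlowSOM clusters. It does not mention the stimulation assay.

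**The concern.** The comparison with and without antigen is a within-child contrast, and it is what makes a T cell response influenza-specific rather than a general level of activation. The method assigned to it relates a T cell variable to HAI titer. That answers a different question: whether the T cell variable varies between children with different titers.

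At stake is the functional part of Aim 3. An analyst who follows 17.d literally obtains no estimate of the antigen effect and no comparison of that effect between arms, which Hypothesis 3 needs. An analyst who sees the gap must choose a model that neither document specifies, possibly with unblinded data in hand.

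**Working it through.** **Inputs.** The conditions, outcome and predictor come from Protocol 17.d. Section 17.d states no sample size, effect size, test or significance level for the cell assays, so there is no plan figure to reproduce.

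**Step 1: the model as written.** For child i, let Y_i1 and Y_i0 be the T cell variable with and without antigen, and H_i the HAI titer at that visit. With HAI as the only predictor:

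E[Y_ic] = b0 + b1·H_i, for c = 0, 1.

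H_i carries no index c, because serum titer does not depend on what is done to the cells in the laboratory. The implied stimulation effect is therefore

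(b0 + b1·H_i) − (b0 + b1·H_i) = 0, whatever b0 and b1 are.

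Fitted to both conditions, the model sets the contrast to zero instead of estimating it. Fitted to the stimulated values alone, it contains no contrast.

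**Step 2: do the flexibility provisions help?** Replace the line by any curve f(H), whether chosen by AIC or fitted as a Gaussian process. The difference is f(H_i) − f(H_i) = 0. Only the shape of the HAI curve changes.

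**Step 3: does the SAP help?** Section 7.5 relates baseline phenotype to later HAI titer. It has no antigen condition, so no replacement exists there.

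**Step 4: illustration.** All inputs here are assumptions:
- child-level SD 1 and measurement SD 0.5 in each condition, so the SD of the within-child difference is √(0.25 + 0.25) = 0.707;
- n = 40, 80 and 160 children, the last being 200 × (1 − 0.20) from Protocol 17.a;
- 2,000 replicates, two-sided 0.05 (the level in SAP 2.5).

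Share of datasets flagged:

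| Case | Analysis | n=40 | n=80 | n=160 |
|---|---|---|---|---|
| Antigen shift 1 SD, no HAI association | HAI slope, stimulated values | 0.051 | 0.043 | 0.048 |
| | HAI slope, both conditions pooled | 0.076 | 0.053 | 0.050 |
| | Paired difference | 1.00 | 1.00 | 1.00 |
| Antigen shift 0.3 SD, no HAI association | HAI slope, stimulated values | 0.047 | 0.048 | 0.059 |
| | Paired difference | 0.76 | 0.97 | >0.99 |
| No antigen shift, child level correlated 0.4 with HAI | HAI slope, stimulated values | 0.64 | 0.90 | 1.00 |
| | HAI slope, both conditions pooled | 0.73 | 0.93 | 1.00 |
| | Paired difference | 0.05 | 0.05 | 0.05 |

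Hand check of the paired row at a shift of 0.3 and n = 40: 0.3 × √40 / 0.707 = 2.68, and Φ(2.68 − 1.96) = Φ(0.72) = 0.76, as simulated. The 0.076 in the pooled row at n = 40 reflects the clustered standard error in a small sample; with no effect of any kind that analysis gave 0.070.

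The table shows what Step 1 implies: the HAI slope and the antigen effect are separate quantities, and one carries no information about the other.

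**The case against.** **17.d is written for estimation.** It names no null hypothesis, test or significance level, and section 17 otherwise works with posterior and credible intervals. This stands. A reader might take the table as a false-positive rate or a power loss of the plan; it is neither. The defect is that the HAI slope does not estimate the antigen effect.

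**The rates are close to tautological.** A slope flags about 5% for an effect it does not contain, and detecting a true HAI association is correct for an association question. This stands, so the figures are illustration only.

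**T cell counts may mean marker-positive cells.** Earlier in 17.d the readout is the frequency of circulating Tfh cells expressing the two markers. A reader might infer that the HAI-marker correlation also uses the wrong variable. The text does not establish that; the regression suits that question if the outcome is clarified. The kinder reading does not rescue the antigen comparison, since counts of marker-positive cells also need a condition term.

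**Speaking of responders implies that a contrast will be used.** If the outcome were the within-child difference and HAI were centred, the intercept would estimate the mean antigen effect; in the simulation at a shift of 0.3 SD and n = 40 it flagged 0.76, equal to the paired analysis. But 17.d defines no such difference and names another outcome.

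**The listed objectives concern the relationship to HAI.** This is largely true. Yet 17.d itself lists the with/without-antigen comparison, Hypothesis 3 compares influenza-specific responses between arms, and relating such a response to HAI first requires defining it.

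**The objective is minor.** It is tertiary in the SAP, whose section 7 is offered as possible exploratory work. This stands and limits the consequence.

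**Conclusion.** The point holds for one of the two questions in the sentence. As written, the regression on HAI titer does not estimate the stimulated-versus-unstimulated difference in ICOS and CD40L expression, and the SAP provides nothing in its place. That conclusion follows from the form of the model and needs no assumed effect size, only that HAI titer is the sole predictor (the only one named) and is shared by both conditions of a child.

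The size in this trial cannot be stated, because the documents give no assay sample size, variance or expected effect.

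A reader might also infer that a significant HAI slope would reflect general immune recovery, with more T cells going along with higher titers, and would be reported as an antigen-specific response. The documents do not support this. The protocol background ties lower titers to GVHD, low CD19+ B cells and early vaccination, not to T cell counts; SAP 7.5 offers only a hypothesis about cell clusters; and no passage says that the HAI slope would be reported as the antigen effect.

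The effect is confined to a secondary (protocol) or tertiary (SAP) mechanistic objective. The primary HAI comparison and the safety conclusions are untouched.

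**What to change.** Replace the method sentence in Protocol 17.d and add the same analysis to SAP section 7:

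1. **Antigen effect.** Model ICOS and CD40L expression on CD4+CXCR5+ cells (on a stated scale, at stated visits) as Y_ic = a0 + a1·C + a2·X + a3·C·X + u_i + e_ic, where C is antigen condition, X is arm (1 = HD-TIV) and u_i is a child effect. Then a1 is the antigen effect under SD-QIV, a1 + a3 the effect under HD-TIV, and a3 the between-arm contrast needed for Hypothesis 3. An equivalent paired-difference analysis would serve.
2. **Relation to titer.** In a separate model, relate the within-child stimulated-minus-unstimulated difference to HAI titer. Either direction of regression is acceptable, and the linear, non-linear and Gaussian-process options can stay here.
3. **Outcome wording.** Say whether T cell counts means marker expression, marker-positive cells or total cells.

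The cost is wording and slightly more analysis work. Both antigen conditions are already planned, so no further blood, samples or assays are needed.

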## 18. Ethics/Protection of Human Subjects:

### a. Ethical Standard:

The investigator(s) will ensure that this study is conducted in full conformity with the principles of the Belmont Report: Ethical Principles and Guidelines for the Protection of Human Subjects of Research of the National

Commission for the Protection of Human Subjects of Biomedical and Behavioral Research (April 18, 1979) and codified in 45 CFR 46, 21 CFR 312, 21 CFR 50, 56, and, if applicable, ICH E6; 62 Federal Regulations 25691 (1997).

**b. Institutional Review Board:**

1. The protocol, informed consent documents, and all types of volunteer educational information must be submitted to the IRB for review and must be approved before the study is initiated.
2. The responsible official for the IRB will sign the IRB letter of approval of the protocol prior to the start of this trial.
3. Should amendments to the protocol be required, the amendments will be written by the study team and submitted to the FDA and IRB.
4. The investigator is responsible for keeping the IRB apprised of the progress of the study and of any changes made to the protocol as deemed appropriate, but at least once a year. The investigator must also keep the IRB informed of any significant adverse events.
5. The study may be discontinued for administrative reasons or if new data about the investigational product/regimen resulting from this or any other studies become available, and/or on advice of the DSMB, DSMC, Investigator, and/or IRB. If a study is prematurely terminated or suspended, the Investigator shall promptly inform the IRB of the reason for termination or suspension.
6. If for any reason the study is prematurely terminated, the Investigator will promptly inform the subject's parent or legal guardian and ensure appropriate therapy and follow-up for volunteers.
7. All key study staff regularly undergo training in human subjects issues conducted by the participating site or their IRBs.

